### **STATISTICAL ANALYTIC PLAN**

EXPOSURES: *Primary:* 1) OSA defined by AHI, i.e. number of apneas + hypopneas/hour of sleep.

*Secondary:* 1) Hypoxia: % sleep time with SaO2 < 90%, 2) Central Sleep Apnea [central apneas/hour of sleep, Central Apnea Index (CAI)], 3) Periodic Breathing (Aims 1 and 2)

OUTCOME: 1) Corrected QT interval (ms) (primary outcome), 2) Quantitated T wave morphology via QT Guard software (ms) (secondary outcome) (Aims 1 and 2)

COVARIATES: Age, sex, race, body mass index (BMI, kg/m^2), anti-arrhythmic/beta blocker/calcium channel blocker/ACE inhibitor/angiotensin receptor blocker/antipsychotic medications, BP, diabetes mellitus, left ventricular ejection fraction (if echocardiographic data available).

#### ***Analytic Method by Aim.***

**Aim 1. Quantify the extent that OSA and hypoxia are associated with corrected QT interval duration.** This aim will be addressed by fitting linear regression models and separately analyzing each OSA variable (primary variable: AHI) to obtain a beta estimate and standard error per 1-unit increase in the OSA exposure. Non-linear effects between OSA and QT duration will be assessed using restricted cubic splines. Knots for the spline will be based on the OSA threshold at which QT prolongation risk increases. Unadjusted and hierarchical adjusted models will be performed using the covariates listed above. The secondary exposure variables (e.g. hypoxia, central apnea index) will be considered in separate models. The secondary outcome of quantitated T wave morphology will be evaluated in separate analyses per the approach described above.

**Aim 2. Examine the effect of OSA (AHI $\geq$ 5) treatment for 3 months on QT interval duration.**

For this subgroup of OSA (AHI $\geq$ 5, estimated to be 50% of n=50) and we will perform t-tests to compare pre- and post- treatment mean outcome (Primary outcome: QT duration) and also novel quantitated T wave morphologic measures. For either outcome for which a departure in normality is found (based on the Shapiro-Wilk test) but a transformation of the outcome can not be found to adequately address the issue, we will use the Wilcoxon signed rank sum test to detect a difference in the distribution of the pre- and post- responses. This assessment is not intended to be confirmatory, but rather to provide estimates of variability and effect sizes to inform future studies/randomized trials. Linear regression models will then be developed to QT interval duration at the 3-month visit by conditioning on baseline QT interval duration, baseline OSA, and time from baseline to 3-month visit. Additional adjusted models will carefully consider the covariates list above.

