## SPECIFIC AIMS

**Aim 1.** To examine the extent that OSA severity and degree of hypoxia are associated with QT interval prolongation and novel T wave morphologic assessments on serial hourly 12-lead ECG collected during overnight polysomnography and also corrected QT interval (QTc) from daytime 12-lead ECG in those predisposed to prolonged QT interval, i.e. those with 1) LQTS, 2) acquired heart disease and 3) arrhythmogenic drugs.

**Hypothesis 1.** We hypothesize that the extent of severity of OSA and degree of hypoxia (defined by the apnea hypopnea index and percentage of sleep time spent <90% respectively) will be associated

with QT interval prolongation and novel T wave morphologic assessments even after consideration of confounding factors including age, sex, race and body mass index. Exploratory analyses will examine the mediation of cardiac substrate (left ventricular ejection fraction) on these associations.

**Aim 2.** To investigate the effect of OSA treatment with 3-month continuous positive airway pressure (CPAP) on QT interval duration as well as novel biomarkers of T wave morphology observed on ECG data collected during overnight polysomnography and also QTc collected from daytime 12-lead ECG in those with LQTS.

**Hypothesis 2.** We postulate that 3-month treatment of OSA will reduce the QT interval and improve novel electrophysiologic markers of ventricular stability in patients who are vulnerable to VTA and sudden cardiac death.

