## **PROTOCOL**

Potential participants will come to the Cleveland Clinic Clinical Research Unit (CRU) for informed consent, eligible participants will undergo a 12 lead electrocardiogram. If the participants is found to have long QT syndrome ( $QT_c \geq 450$  in men and  $\geq 470$  in women) they will continue on in the study. If they are found to not have long QT syndrome they will exit the study. If continuing on in the study the participant will undergo a fasting venipuncture and blood pressure measurements. The participant will then be shown how to use the portable sleep study hook-up and continuous 12-lead ECG monitoring to be monitored in the home setting. The sleep study and ECG monitors will be returned by a courier service the next morning.

Those participants who are identified to have OSA (apnea hypopnea index  $\geq 5$ , estimate 50% of those recruited) on the portable sleep monitoring will be invited to wear CPAP for 2-3 months with a follow up visit with repeat portable polysomnographic and continuous electrophysiologic assessments and CRU visit for bloodwork and blood pressure.

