#### *Continuous Positive Airway Pressure Intervention*

Subjects randomized to CPAP will be provided with an Autopap REMstar device (Philips-Respironics, Inc, Murrysville, PA) with integrated humidifier, set at a pressure range of 4-20 cm H2O, with auto-titration according to the device's algorithm for detecting airflow limitation which provided wireless transmission of usage information to our research team.

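### Aim 2 asks for the effect of CPAP on QT, but no term in its analyses measures treatment received, and the CPAP usage information sent to the team is not used

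*Combined protocol and SAP*

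**What the plan says.** The Specific Aims set the question for Aim 2: "To investigate the effect of OSA treatment with 3-month continuous positive airway pressure (CPAP) on QT interval duration". Future Directions repeats that the study is to supply an effect size for OSA treatment.

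The Protocol section says who is treated and followed. Participants with an AHI of at least 5 on the portable study "will be invited to wear CPAP for 2-3 months with a follow up visit". It describes no follow-up visit for anyone else. Entry requires a QTc of at least 450 in men or 470 in women on the screening ECG.

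The Aim 2 analysis opens with the OSA subgroup, "estimated to be 50% of n=50", so about 25 people. In that subgroup "we will perform t-tests to compare pre- and post- treatment mean outcome", with a signed-rank test as fallback. A linear regression of 3-month QT follows, "conditioning on baseline QT interval duration, baseline OSA, and time from baseline to 3-month visit". Further models may draw on the covariate list in the Statistical Analytic Plan ("COVARIATES: Age, sex, race, body mass index", then cardiovascular and antipsychotic drugs, blood pressure, diabetes and ejection fraction). CPAP acceptance and CPAP use are not on the list.

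The CPAP section says that the device provides "wireless transmission of usage information to our research team". The same section has wording that fits a different design: "Subjects randomized to CPAP will be provided with an Autopap REMstar device". The Aim 2 power statement describes a third, a two-sample comparison of 25 people with OSA and 25 without.

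**The concern.** A regression usually follows a pre/post test in order to say more about the treatment. This one cannot. Everyone in it is offered CPAP, and its terms are two baseline measurements and elapsed time. Elapsed time runs over roughly 2-3 months and is the same for a person who uses the device every night as for one who leaves it in the box.

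The only treatment information left is therefore the mean change. That mean would also move with any drift between visits, and it would fall by regression to the mean, because people are admitted on a high QTc reading. Aim 2 is meant to hand an effect size to a later randomised trial. Without a record of how much CPAP was used, the planners of that trial cannot tell what exposure the observed change corresponds to, or whether it rises with exposure at all. The data to describe this reach the team but appear in no analysis.

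**Working it through.** **The plan's own figure.** The plan gives no number for this point. The nearest is the Aim 2 detectable difference, 0.46 SD at 80% power and 0.53 SD at 90%, for 25 v 25 with a two-sided alpha of 0.05. The exact t calculation gives 0.81 and 0.94 SD, so the stated pair is not reproduced. That is a separate matter, and nothing below depends on it.

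**What the written regression can identify.** With centred covariates, its intercept minus the mean baseline QT is the mean pre/post change, which the t-test already gives. A simulation shows what that quantity contains. All inputs are assumptions: n=25, true QTc with mean 470 ms and between-person SD 25 ms, within-person SD 12 ms, one entry threshold of 460 ms, and use uniform on 0-8 h (mean 4 h), unrelated to prognosis. The CPAP effect, where present, is -2.5 ms per hour, or -10 ms at mean use.

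| Truth | Change from the written model | Slope on use, if added |
|---|---|---|
| No CPAP effect, no drift | -3.0 ms | about 0 |
| CPAP effect averaging -10 ms | -13.0 ms | -2.5 ms/h |
| No CPAP effect, drift of -10 ms | -13.0 ms | about 0 |

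The first row is regression to the mean alone. The second and third rows look the same to the written model and differ only in the usage slope. The standard error of that slope was about 1.6 ms/h. Because use was simulated as unrelated to prognosis, this is the favourable case.

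**Precision of a usage slope.** Inputs: n=25 from the plan; n=20 is 25 x 0.8, applying the upper end of the 10-20% drop-out that the plan reports for the group's earlier trials. The SD of QTc change (20 ms) and the SD of mean use (2-3 h) are assumptions.

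SE = 20 / (SD of use x sqrt(n - 1))

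- n=25, SD of use 3 h: 20 / (3 x 4.899) = 1.36 ms/h
- n=20, SD of use 2 h: 20 / (2 x 4.359) = 2.29 ms/h

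95% half-width with use added to the three written terms (df = n - 5):

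- n=25: 2.086 x 1.36 = 2.84 ms/h
- n=20: 2.131 x 2.29 = 4.89 ms/h

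With only baseline QTc and use in the model (df = n - 3) these become 2.82 and 4.84 ms/h.

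**Against a plausible effect.** A 10 ms effect at 4-6 h of use (assumption) is a slope of 10/6 = 1.7 to 10/4 = 2.5 ms/h, below the half-width in every case. Power to detect it is about 10% to 42%. Seen another way, 80% power with four predictors needs a partial correlation between use and follow-up QT of about 0.51 (n=25) to 0.56 (n=20).

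**Split at median use.** With SD 20 ms, the difference in mean change between halves has a 95% half-width of:

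- 12 v 13: 2.069 x 20 x sqrt(1/12 + 1/13) = 16.6 ms
- 10 v 10: 2.101 x 20 x sqrt(1/10 + 1/10) = 18.8 ms

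Such a split can only be descriptive.

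**The case against.** The strongest reply is that the pre/post comparison, and not the regression, is the plan's stated estimator for Aim 2, and that the plan calls this assessment non-confirmatory. Both are true. A reader might infer that the regression says nothing at all about treatment, or that a usage term would let it estimate the CPAP effect. Neither follows. Its intercept carries the mean change, and that mean is confounded because there is no untreated OSA group. A usage term does not cure this: use is self-selected, and people who use CPAP well may differ in other ways.

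A reader might also infer that non-users dilute the mean and so mislead planning. For example, if 30-50% barely used CPAP (assumption), a 10 ms change under use would appear as 5-7 ms. This is weak as a complaint. A later trial analysed by assignment will also contain non-users, so the all-participants mean is the relevant planning quantity, subject to its lack of a control. A users-only figure could leave that trial too small. The documents give no rate of non-use. Because the follow-up visit is tied to the CPAP invitation, people who decline may never enter the mean.

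Two readings of the design need an answer. If CPAP is in fact randomised, the missing term is the assigned arm. If people without OSA are followed and included, a yes/no OSA term would coincide with the CPAP offer, so treatment would still be confounded with OSA. The restriction of the regression to the OSA subgroup is read from the opening of the Aim 2 paragraph and the visit plan; the regression sentence does not repeat it.

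What stands is narrower: nothing in the analysis measures treatment received, and information that could describe it goes unused.

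**Conclusion.** The point holds as an inexpensive improvement to a pilot analysis. As written, the Aim 2 regression adds no treatment contrast to the pre/post mean, and the transmitted usage information enters no analysis. An exploratory usage slope would be the only within-sample contrast in treatment received that a single-arm design offers.

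Its value is limited. With the assumed SDs and n=20-25, the standard error is about 1.4-2.3 ms/h and the 95% half-width about 2.8-4.9 ms/h. A reader might take that as enough for a planning range. It is not, since it exceeds the 1.7-2.5 ms/h slope that a 10 ms effect at 4-6 h would imply. The slope is an association open to healthy-adherer bias. Only an untreated OSA comparator would separate CPAP from drift and regression to the mean without relying on self-selected use.

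The documents say that usage information is transmitted; they do not say that it is recorded by night. Mean use per night is therefore an assumption about what can be extracted.

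**What to change.** In the Aim 2 analysis:

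1. Keep the pre/post change in all participants as the main result, and state that it mixes CPAP with drift and regression to the mean.
2. Report how many accepted CPAP and the distribution of use.
3. Prespecify one exploratory regression of follow-up QTc on baseline QTc and mean CPAP use. Report the slope with its 95% confidence interval and no test, and label it an association.
4. Show the pre/post change by level of use, descriptively.
5. Reconcile the randomisation wording in the CPAP section, and the OSA versus no-OSA comparison in the power statement, with the single-arm design in the Protocol and Aim 2 sections. If CPAP is randomised, put the assigned arm in the model.

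The cost is one extra model and one table, with no new visits, devices or participants. The risk is that an imprecise, self-selected slope is read as a treatment effect; the label and the interval are there to prevent that.

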#### **POWER BY AIM.**

**Specific Aim 1.** A sample size of 50 will be able to detect 0.59 standard deviations with 80% power (and 0.62 with 90% power), assuming a 2-sided alpha level of 0.05 which is sufficient for generation of pilot data.

**Specific Aim 2.** Using a two-sample t-test (2-sided 0.05 alpha-level) to test for a difference in mean variation between the SDB (AHI $\geq$ 5) and no SDB groups, a sample size of 50 (25 with OSA and 25 without OSA) will detect mean differences within 0.46 standard deviations with 80% power and 0.53 standard deviations with 90% power.

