## **METHODS**

### ***Participant Eligibility Criteria and Process for Recruitment***

We plan to recruit 50 patients with QT prolongation as identified by ICD 10 426.82 from the Cleveland Clinic. At the Cleveland Clinic, we will utilize the Knowledge Program query tool and EResearch along with [name] Registry: Cleveland Clinic internal registry for inherited arrhythmias (IRB: 16-1094) platforms to identify potential recruits. Those patients with congenital LQTS or QT prolongation related to acquired heart disease or arrhythmogenic drugs will be eligible. Approximately ~500 patients/year (42/month) with QT prolongation are evaluated at the Cleveland Clinic. Assuming 50% meet eligibility criteria and 50% of those are interested then ~n=125 patients will be recruited/year (n=16/month over 8 months). This translates into n~150 potential participants over the 8-month recruitment period which exceeds the n=50 cases required to meet sample size requirements.

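### The two Aim 1 detectable effects (0.59 SD at 80% power, 0.62 SD at 90%) cannot both hold at n=50, and the sentence names no test and no SD

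*Combined protocol and SAP*

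**What the plan says.** Under POWER BY AIM, Specific Aim 1, the combined protocol and SAP states: "A sample size of 50 will be able to detect 0.59 standard deviations with 80% power (and 0.62 with 90% power". It adds a two-sided alpha of 0.05 and concludes that the size is one "which is sufficient for generation of pilot data". The sentence gives n, alpha, sidedness and a unit. It gives no test, no grouping and no variable to which the SD belongs.

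The Aim 1 analysis is described under Analytic Method by Aim: "This aim will be addressed by fitting linear regression models and separately analyzing each OSA variable", with AHI as the primary exposure, "to obtain a beta estimate and standard error per 1-unit increase in the OSA exposure". It continues: "Unadjusted and hierarchical adjusted models will be performed using the covariates listed above". The primary outcome is corrected QT in ms. The document gives no SD for QTc or for AHI.

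The recruitment section treats 50 as a derived requirement. It says that the expected pool "exceeds the n=50 cases required to meet sample size requirements".

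**The concern.** Moving from 80% to 90% power at the same n and alpha should raise the detectable effect by about 16%. Here it rises by about 5%. The gap is too large for rounding, so at least one of the two figures must be wrong.

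The missing test makes this worse. The planned analysis estimates a slope on a continuous exposure, whereas an effect in SDs with no further description could be a difference between groups, a within-person change or a standardized slope. This is the only place where the Aim 1 size requirement is quantified. As written, the reader cannot learn what association between AHI and QTc 50 participants can detect. That information would be useful for the later studies and the grant application that the plan says these data will support.

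**Working it through.** **Inputs from the document.** n = 50; two-sided alpha 0.05; 0.59 SD at 80% power; 0.62 SD at 90% power (POWER BY AIM, Specific Aim 1). Planned analysis: linear regression of QTc on AHI (Analytic Method by Aim, Aim 1).

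**Step 1: the ratio.** For a standardized mean difference or slope, the detectable effect is (z for alpha + z for power) × SE. The SE depends on n and allocation, which are the same for both figures, so it cancels:

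- Required ratio: (1.960 + 1.282)/(1.960 + 0.842) = 3.2415/2.8016 = 1.157.
- Stated ratio: 0.62/0.59 = 1.051.
- Rounding limits: 0.615/0.595 = 1.034 to 0.625/0.585 = 1.068.

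**Step 2: what each figure implies for the other.**

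- If 0.59 is right at 80%, the 90% figure is 0.59 × 1.157 = 0.683 (0.677 to 0.688 with rounding). Power at 0.62 is then Φ(2.802 × 0.62/0.59 − 1.960) = 0.837 (0.825 to 0.849).
- If 0.62 is right at 90%, the 80% figure is 0.62/1.157 = 0.536 (0.532 to 0.540). Power at 0.59 is then Φ(3.242 × 0.59/0.62 − 1.960) = 0.870 (0.859 to 0.880).

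**Step 3: in participants.** By the normal approximation, a one-sample test needs (2.802/0.59)² = 22.5 for 0.59 SD at 80% power and (3.242/0.62)² = 27.3 for 0.62 SD at 90% power. Two equal groups need four times as many in total: 90.2 and 109.3. Either way the 90% figure needs (1.157/1.051)² = 1.21 times as many participants (1.17 to 1.25 with rounding), so a single n cannot give both.

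**Step 4: attempts to reproduce the plan's pair** (noncentral t, two-sided 0.05):

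| Reading | Detectable, 80% / 90% | Power at 0.59 / 0.62 |
|---|---|---|
| One-sample or paired, n=50 | 0.404 / 0.468 | 0.983 / 0.990 |
| Paired, n=25 | 0.584 / 0.676 | 0.808 / 0.845 |
| Two-sample, 25 vs 25 | 0.809 / 0.936 | 0.534 / 0.575 |

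None gives both figures. Paired n=25 comes near 0.59 at 80%, but it is neither n=50 nor the Aim 1 analysis, and it misses the 90% figure. A correlation scale does not help: r = 0.59 at 80% power pairs with r = 0.655 at 90%, a ratio of 1.11.

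**Step 5: what the planned regression can detect.** By Fisher z with k single-df covariates, SE = 1/√(n − 3 − k) and r = tanh(z-sum × SE):

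- k = 0: tanh(2.802/√47) = 0.387 and tanh(3.242/√47) = 0.440.
- k = 4 (assumption: one df each for the "confounding factors including age, sex, race and body mass index" of Hypothesis 1): tanh(2.802/√43) = 0.403 and tanh(3.242/√43) = 0.458.
- k = 13 (assumption: every item in the SAP covariate list at one df, medication classes counted separately): tanh(2.802/√34) = 0.447 and tanh(3.242/√34) = 0.505.

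The k = 4 and k = 13 values are partial correlations. A check by numerical integration for a normally distributed exposure gave 0.384 and 0.437 for k = 0, and 0.399 and 0.453 for k = 4.

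**Comparison within the section.** The Aim 2 pair, "0.46 standard deviations with 80% power and 0.53 standard deviations with 90% power", has ratio 0.53/0.46 = 1.152 (1.129 to 1.176 with rounding), which agrees with 1.157. Its values are a separate matter: the 25 vs 25 t-test named there gives 0.81 and 0.94.

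**The case against.** The 1.157 ratio belongs to a single-df effect on an SD scale. If the authors had powered an overall regression test on the multiple-R scale, the ratio would be smaller: 1.10 with 4 predictors and 1.077 with 14. Counting AHI plus 13 covariates gives 14 predictors, for which the detectable R is 0.576 and 0.620. The second value matches the plan's 0.62, and the first is within about 0.015 of 0.59. This is a fair caution against calling 1.157 universal. It does not rescue the sentence: the stated unit is standard deviations, 0.576 does not round to 0.59, and with 15 predictors the pair becomes 0.585 and 0.629, which still does not match both figures.

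It can also be said that a correlation-based replacement chooses an effect scale for the authors, and that a four-covariate example understates the cost of the fully adjusted models. Both points have some force. The fix therefore leaves room for another named test and shows the longer covariate list as well. Partial correlations also do not translate directly to ms per AHI unit, because covariates that explain QTc variance can reduce the detectable slope.

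Finally, this is a pilot, the plan claims no more than pilot adequacy, and the section on pitfalls already concedes limited power for subgroups. This lowers the importance of the point. It excuses a small n, but not two incompatible statements about what that n can detect.

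**Conclusion.** The concern holds. Read in the stated unit, the two Aim 1 figures are incompatible: the ratio is 1.05 (at most 1.068) where 1.157 is required. In power terms the gap is about 6 points if 0.59 is kept (84% rather than 90%), or about 7 points if 0.62 is kept (87% rather than 80%). This conclusion needs no assumption about the SD or the allocation, only that the effect is a standardized difference or slope, as the unit indicates. The document does not show which figure is wrong, or whether both are. The missing test and SD are a second, independent gap in the same sentence. The point should be fixed, but it does not threaten the study: no decision rule uses the figures, and sample size and conduct stand as they are.

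**What to change.** Remove 0.59 and 0.62 and tie the statement to the planned analysis. Suggested text: *With n=50 and a two-sided 0.05 test, the AHI slope in the unadjusted linear regression has 80% power for a correlation with QTc of about 0.39 and 90% power for about 0.44. Adjusted models detect only larger partial correlations: for example, about 0.40 and 0.46 with age, sex, race and BMI at one df each, or about 0.45 and 0.50 with 13 single-df covariates.*

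To express the unadjusted figure in ms per unit of AHI, multiply the correlation by SD(QTc)/SD(AHI) and state the SDs assumed, since the document gives neither. If a different test was intended, name it, say which SD is the unit, and recompute both figures from it.

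The cost is wording only. Sample size, conduct and analysis do not change.

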## ***Clinical Trial Experience/Recruitment and Retention***

Our group has conducted several clinical trials and interventional studies utilizing CPAP involving collaboration with sleep medicine and cardiologists/electrophysiologists for which we have either met or exceeded recruitment goals and have had expected retention (drop out range: 10-20%). (*NIH/NHLBI HL079114: Oxidative Stress in Sleep Apnea and Cardiac Disease, NHLBI 1RC2HL101417: Phase II Trial of Sleep Apnea Treatment to Reduce Cardiovascular Morbidity, NHLBI R01 HL 109493: Elucidation of the Risk of Sleep Apnea in Atrial Fibrillation*).

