#### *Inclusion Criteria:*

1) Clinical diagnosis of QT prolongation as described above, 2) Age 18-75 years, 3) Individuals able to participate in at least 2 overnight sleep and physiologic assessments over a 3 month period.

*Exclusion Criteria:* 1) Use of specific OSA treatments (CPAP, oral appliances), 2) Use of supplemental oxygen, 3) Severe chronic insomnia, 4) Circadian rhythm disorder (e.g. shift work sleep disorder, delayed or advanced sleep phase syndrome), 5) Insufficient sleep syndrome defined by reported sleep duration < 4 hrs, 4) Unstable medical conditions (e.g., new onset or changing angina, a myocardial infarction or congestive heart failure exacerbation documented within the previous 3 months, uncontrolled hypertension (BP>170/110), uncontrolled diabetes mellitus (HbA1c>9.0), uncontrolled hypo- or hyperthyroidism), 5) Psychiatric disorders which are inadequately treated, 6) Compromised competence, 7) Alcohol abuse (currently drinks >5 alcoholic drinks/day), 8) Inability to provide informed consent, 9) Illicit drug use over last 6 months. *Rationale for criteria:* Patients with sleep disorders will be excluded as other sleep disorders may influence arrhythmogenesis. Those on treatment for SDB will be excluded because treatment would preclude assessment of OSA pathophysiologic effects on QT biomarkers.

Those with unstable medical conditions or rapid or uncontrolled heart rate will be excluded due to safety reasons.

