### **Future Directions**

The goals of the application are to overcome existing knowledge gaps in understanding the influence of OSA on cardiac electrophysiology, namely QT prolongation, which predisposes to VTA and cardiac death. The pilot data generated will be key in elucidating the impact of OSA on predisposing to cardiac vulnerability in those who are predisposed, i.e. have congenital or acquired QT interval prolongation. Data generated will provide important information on effect size of OSA treatment on QT interval prolongation which will inform future studies.

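### The Aim 2 detectable differences (0.46 and 0.53 SD) do not follow from 25 versus 25, belong to a different test from the planned pre/post comparison, and use an undefined SD

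*Combined protocol and SAP*

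**What the plan says.** - **Power by Aim, Specific Aim 2.** The test is a two-sample t-test at two-sided alpha 0.05, used "to test for a difference in mean variation between the SDB" group (AHI of 5 or more) and the group without it. The plan states that "a sample size of 50 (25 with OSA and 25 without OSA) will detect mean differences within 0.46 standard deviations with 80% power". The figure for 90% power is 0.53 SD.
- **Analytic Method by Aim, Aim 2.** In the OSA subgroup, put at 50% of 50, "we will perform t-tests to compare pre- and post- treatment mean outcome (Primary outcome: QT duration"). The fallback for non-normal data is a Wilcoxon signed rank test on the pre and post responses. A regression of 3-month QT on baseline QT, baseline OSA and time between visits follows. The section adds: "This assessment is not intended to be confirmatory, but rather to provide estimates of variability and effect sizes".
- **Protocol.** Participants found to have OSA "on the portable sleep monitoring will be invited to wear CPAP for 2-3 months with a follow up visit" and repeat recordings. No follow-up visit is described for the others.
- **Inclusion Criteria.** All participants must be "Individuals able to participate in at least 2 overnight sleep and physiologic assessments over a 3 month period".
- **Future Directions.** "Data generated will provide important information on effect size of OSA treatment on QT interval prolongation which will inform future studies".
- **Clinical Trial Experience/Recruitment and Retention.** The group's earlier CPAP studies "have had expected retention (drop out range: 10-20" per cent).

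**The concern.** Three things are wrong with the power statement.

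1. A two-sample t-test with 25 per group cannot detect a difference as small as 0.46 SD with 80% power.
2. The statement compares people with and without OSA, whereas Aim 2 asks what CPAP does within people who have OSA.
3. The plan does not say whether its SD is that of a single QTc reading, of the within-patient change, or of something else. The phrase about mean variation does not settle it.

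This is the only statement of how sensitive Aim 2 is, and the aim exists to supply an effect size for later trials. A reader who trusts it would think the pilot can reliably show an effect of about half an SD, and could read a null result as stronger evidence than it is.

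**Working it through.** **Inputs from the documents.** Two-sided alpha 0.05; 25 versus 25 (Power by Aim); about 25 participants in the pre/post analysis (Aim 2 method); drop-out of 10-20% in earlier studies. No SD in ms and no pre-post correlation r are given, so r is treated below as an assumption.

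**Step 1. The stated test.** For n per group and standardized difference d, the t statistic has 2n − 2 degrees of freedom and noncentrality d·√(n/2). With n = 25, df = 48, the critical value is 2.011 and √(25/2) = 3.536.

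- d = 0.46: noncentrality 1.63, power 35.7% (claimed 80%).
- d = 0.53: noncentrality 1.87, power 45.1% (claimed 90%).
- Solving for d: **0.81 SD** at 80% power and **0.94 SD** at 90%.

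The plan's figures are not reproduced. Variants tried:

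| Variant | 80% power | 90% power |
|---|---|---|
| Stated in the plan | 0.46 | 0.53 |
| 25 vs 25, two-sided | 0.81 | 0.94 |
| 25 vs 25, normal approximation | 0.79 | 0.92 |
| 25 vs 25, one-sided | 0.71 | 0.84 |
| 50 vs 50, two-sided | 0.57 | 0.65 |
| 75 vs 75, two-sided | 0.46 | 0.53 |
| Paired, 39 pairs (SD of change) | 0.46 | 0.53 |

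At 75 per group, power at the stated effects is 79.9% and 89.7%; at 76 it is 80.4% and 90.1%. Neither 75 per group nor 39 pairs is a sample size in the plan.

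**Step 2. The planned test.** A paired t-test with n pairs has n − 1 degrees of freedom and noncentrality d·√n, where d is in SDs of the within-patient change. The 95% CI half-width for the mean change is t(0.975, n − 1)/√n in the same unit; for 25 pairs this is 2.064/5 = 0.41.

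| Pairs | 80% power | 90% power | 95% CI half-width |
|---|---|---|---|
| 25 | 0.58 | 0.68 | 0.41 |
| 22 | 0.63 | 0.73 | 0.44 |
| 20 | 0.66 | 0.76 | 0.47 |

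The rows for 22 and 20 apply the 10-20% drop-out: 25 × 0.9 = 22.5 and 25 × 0.8 = 20.

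**Step 3. The unit.** If the pre and post SDs are equal, SD of change = raw SD × √(2(1 − r)). For 25 pairs, in raw QTc SDs:

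| Assumed r | 80% power | 90% power |
|---|---|---|
| 0.5 | 0.58 | 0.68 |
| 0.6 | 0.52 | 0.60 |
| 0.7 | 0.45 | 0.52 |
| 0.8 | 0.37 | 0.43 |

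The correlation needed to reach a target raw difference is r = 1 − (target/d)²/2:

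- 25 pairs: 1 − (0.46/0.584)²/2 = 0.69, and 1 − (0.53/0.676)²/2 = 0.69.
- 22 pairs: 0.73. 20 pairs: 0.76.
- Between-group comparison of change, 25 versus 25: 1 − (0.46/0.809)²/2 = 0.84, and 1 − (0.53/0.936)²/2 = 0.84.

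**Side check on recruitment** (Participant Eligibility Criteria and Process for Recruitment). 500 × 0.5 × 0.5 = 125 a year, and 125 × 8/12 = 83 in 8 months, against about 150 stated. The quoted 16 a month seems to be 125/8 (15.6), a year's total spread over 8 months. Even 83 exceeds the 50 required.

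**The case against.** The strongest reply is that the figures may be right in a unit the plan does not spell out. If mean variation means change over time and the SD is that of one QTc reading, a single correlation near 0.84 (about 0.82 with baseline adjustment) yields both 0.46 and 0.53 from 25 versus 25. The regression on baseline QT and OSA, and the entry criterion of two overnight assessments for everyone, leave room for such a contrast. This stands only as a possibility. No correlation appears in the documents, a comparison of change needs second recordings in people without OSA, and the follow-up visit is described only for those with OSA. If that was the intention, the assumption has to be written down, so the text needs correcting either way.

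A second reply is that little depends on the number: Aim 2 is an estimation exercise, the plan concedes limited power, and no decision rule uses 0.46 or 0.53. That is fair and limits the severity.

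A third is that 25 pairs is itself optimistic. Participants are only invited to use CPAP, and the Specific Aims describe Aim 2 as being in those with LQTS, which read narrowly would mean fewer pairs. For illustration, 15 pairs would detect 0.78 and 0.90 SD of change. This also stands, and it is a reason to present 25 pairs as the number if every expected OSA participant takes up CPAP and returns.

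**Conclusion.** The concern holds and should be fixed. For the test it names, the statement is wrong: the detectable differences are 0.81 and 0.94 SD, not 0.46 and 0.53, and power at the stated effects is 36% and 45%. This takes the SD to be that of the variable tested, the ordinary reading of a two-sample t-test. For the test that will be run, the statement cannot be interpreted. That test detects 0.58 and 0.68 SD of the within-patient change with 25 pairs. Whether this is better or worse than the plan's figures cannot be said without r, because the units differ. The result treats the pre/post t-test as paired, which the signed rank fallback implies. Because Aim 2 is non-confirmatory, the consequence is a misstated sensitivity and nothing more.

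**What to change.** Replace the Aim 2 power text with wording such as:

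> Aim 2 compares QTc before and after CPAP within participants who have AHI of 5 or more, expected to number about 25 if all take up CPAP and return. A paired two-sided 0.05 t-test with 25 pairs detects 0.58 SD of the within-patient change with 80% power and 0.68 SD with 90%. With 10-20% drop-out (22 to 20 completers) the figures are 0.63 to 0.66 and 0.73 to 0.76. The half-width of the 95% confidence interval for the mean change is 0.41 SD of the change with 25 pairs and 0.44 to 0.47 with 22 to 20.

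In addition:

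- If results are to be expressed in raw QTc SDs, state the assumed correlation and multiply by √(2(1 − r)).
- Remove the comparison of OSA with no OSA from the Aim 2 power text. If that contrast is wanted, for example at baseline, say so and give 0.81 and 0.94 SD.
- State whether participants without OSA have a second recording.
- Correct the 8-month recruitment forecast to about 83, a minor point.

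The cost is a change of text plus one clarification of the follow-up schedule. It needs no extra patients and no change to the planned analysis.
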